4.6.2.2. Common Adverse Events

The counts and percentages of participants with TEAEs, overall and common (common TEAEs occurred in $\geq 5\%$ of participants in any treatment group before rounding), will be summarized by treatment using MedDRA PT. Events will be ordered by decreasing frequency.

4.6.3. Additional Safety Assessment

4.6.3.1. Deaths

A listing of all deaths during the study will be provided. The listing will include participant identification including the treatment group, site number, participant number, date of death, age at the time of enrollment, sex, cause of death as reported by investigator, cause of death as adjudicated by CEC, etc.

4.6.3.2. Other Serious Adverse Events

The counts and percentages of participants who experienced an SAE (including deaths and SAEs temporally associated with or preceding deaths) during the postbaseline period will be summarized by treatment using MedDRA PT nested within SOC. Events will be ordered by decreasing frequency within SOC. The SOC will be in alphabetical order.

A listing of all SAEs will be provided. The listing will include treatment, participant identification including the site number and participant number, date of event, age at the time of enrollment, sex, MedDRA SOC and PT, reported term, severity, outcome, relationship to study drug, time from first dose of study drug to the event, AE start date, AE end date, severity, and action taken related to study treatment.

4.6.3.3. Other Significant Adverse Events

The counts and percentages of participants who discontinued from study treatment or study due to an AE during the postbaseline period may be summarized by treatment group using MedDRA PT nested within SOC. Events will be ordered by decreasing frequency within SOC.

Pulse (bpm) (Supine or sitting)	< 50 and decrease from baseline ≥ 15	> 100 and increase from baseline ≥ 15

Abbreviations: BP = blood pressure; bpm = beats per minute.

In addition, the following analyses will be conducted by treatment:

- counts and percentages of participants who had resting heart rate increases from baseline at 2 or more consecutive visits of more than 10 bpm and/or 20 bpm
- counts and percentages of participants who had resting heart rate at any postbaseline visit increases from maximum baseline ≥ 20 bpm
- counts and percentages of participants who had at least 1 resting heart rate at any postbaseline visit exceeding 100 bpm, and
- counts and percentages of participants who had at least 1 resting heart rate exceeding 100 bpm occurring at 2 or more consecutive study visits.

4.6.3.5. Electrocardiograms

Summary statistics by treatment and by nominal visit will be provided for ECG parameters (heart rate, PR, QRS, QT, and QT corrected QTcF [QTcF = $QT / RR^{0.333}$]). When the QRS is prolonged (eg, a complete bundle branch block), QT and corrected QT interval should not be used to assess ventricular repolarization. Thus, for a particular ECG, the following will be set to missing (for analysis purposes) when QRS is ≥ 120 msec: QT and QTcF.

Change from baseline to postbaseline values for ECG parameters (heart rate and PR) will be summarized for participants who have both a baseline and at least 1 postbaseline result. Only scheduled measurements will be included in the mean change analyses.

The criteria for identifying participants with treatment-emergent quantitative ECG abnormalities is based on [Table GPHL.4.6](#).

The counts and percentages of participants who meet the following criteria at any time during the entire study period (including the safety follow up period) will be summarized by treatment group:

- treatment-emergent ECG abnormalities as listed in [Table GPHL.4.6](#)
- QT greater than 500 msec
- QTcF greater than 500 msec, and

- treatment-emergent increase from the maximum baseline in QTcF interval of greater than 30 msec, 60 msec, or 75 msec. Maximum baseline will be the maximum nonmissing observation in the baseline period. The maximum value during the treatment period will be analyzed. Scheduled and unscheduled measurements will be included.

Table GPHL.4.6. Selected Categorical Limits for ECG Data

Parameter	Low		High	
	Males	Females	Males	Females
Heart Rate (bpm)	<50 and decrease ≥ 15	<50 and decrease ≥ 15	>100 and increase ≥ 15	>100 and increase ≥ 15
PR Interval (msec)	<120	<120	≥ 220	≥ 220
QRS Interval (msec)	<60	<60	≥ 120	≥ 120
QTcF (msec)	<330	<340	>450	>470

Abbreviations: bpm = beats per minute; ECG = electrocardiogram; QTcF = Fredericia's corrected QT interval.

4.6.3.6. Clinical Laboratory Evaluation

Limits from the performing lab will be used to define low and high. Descriptive summaries by treatment and by nominal visit will be provided for the baseline and postbaseline values as well as the change from baseline values. The associated descriptive will be presented in SI units and in CN units.

Observed and change from baseline values for each visit may be displayed in plots for participants who have both a baseline and at least 1 postbaseline scheduled measurement. Baseline is defined in [Table GPHL.4.1](#). Unscheduled measurements will be excluded from plots.

A shift table will be provided including unscheduled measurements. The shift table will include the number and percentage of participants within each baseline category (low, normal, high, or missing) versus each postbaseline category (low, normal, high, or missing) by treatment. The proportion of participants shifted will be compared between treatments using Fisher's exact test.

For qualitative laboratory analytes, the number and percentage of participants with normal and abnormal values may be summarized by treatment.

A listing of abnormal findings will be created for laboratory analyte measurements, including qualitative measures. The listing will include participant identification, treatment group, laboratory collection date, study day, analyte name, and analyte finding.

The MMRM model or ANCOVA (if MMRM model is not applicable) will be used for the analysis during the treatment period for the continuous measurements for selected lab tests.

4.6.4. Patient Narratives

Patient narratives will be provided for all participants who experience any of the following "notable" events:

- death

- SAE
- permanent discontinuation of study treatment due to AEs
- pregnancy

Patient narratives (patient level data and descriptive paragraph) will be provided for participants in the randomized population with at least 1 notable event.

4.6.5. Special Safety Topics

For AESI or special safety topics, the counts and percentages of participants will be summarized by treatment and PT with decreasing frequency. Individual participant level data may be presented. Displays with individual participant level data may be created using various formats, such as a customized listing and/or a customized graphical participant profile. Adverse events of special interest are defined in each section of special safety topics, where applicable.

4.6.5.1. Exocrine Pancreas Safety

4.6.5.1.1. Pancreatic Enzyme

Observed pancreatic enzyme data (p-amylase and lipase) will be summarized by treatment.

The counts and percentages of participants with maximum postbaseline pancreatic enzyme value exceeding the following thresholds will be provided by baseline pancreatic enzyme value (\leq ULN, $>$ ULN), and postbaseline: $\leq 1 \times$ ULN, $(>1$ to $\leq 3) \times$ ULN, $(>3$ to $\leq 5) \times$ ULN, $(>5$ to $\leq 10) \times$ ULN, $>10 \times$ ULN.

An MMRM analysis will be used to analyze each pancreatic enzyme with a log transformed (postbaseline measure/baseline measure) response variable and treatment, nominal visit, treatment-by-nominal visit interaction as fixed effects.

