9.4. Statistical Analyses

9.4.1. General Considerations

Statistical analysis of this study will be the responsibility of Lilly or its designee. Any change to the data analysis methods described in the protocol will require an amendment ONLY if it changes a principal feature of the protocol. Any other change to the data analysis methods described in the protocol, and the justification for making the change, will be described in the SAP or the clinical study report (CSR). Additional exploratory data analyses may be conducted as deemed appropriate.

Unless otherwise noted, all tests of treatment effects will be conducted at a 2-sided alpha level of 0.05, and the confidence interval will be given at a 2-sided 95% level. In statistical summaries and analyses, data will be analyzed as randomized.

Unless specified otherwise, efficacy analyses will be conducted using efficacy analysis set (EAS) and safety analyses will be conducted using safety analysis set (SS). Baseline is defined as the last nonmissing data collected prior to or at randomization.

Summary statistics for continuous measures will include sample size, mean, SD, median, minimum, and maximum. The analysis model to make comparisons among treatment groups relative to continuous measurements assessed over time will be a mixed model for repeated measures (MMRM), with terms of treatment, visit, treatment-by-visit interaction, stratification factors and baseline measurement as a covariate. An unstructured covariance structure will model relationship of within-patient errors.

Kaplan-Meier method will be used for estimation of cumulative event-free survival rates over time, and cox proportional hazards regression analysis will be used to compare hazard rates among treatments.

Summary statistics for categorical measures (including categorized continuous measures) will include sample size, frequency, and percentages. Logistic regression will be used to examine the treatment difference in binary efficacy outcomes if there is a need to adjust for covariates. Otherwise, Fisher's exact test will be used to examine the treatment difference in categorical outcomes.

Summary statistics for discrete count measures will include sample size, mean, SD, median, minimum, and maximum. The negative binomial regression model will be used for the treatment comparison of discrete count measures.

Other statistical methods may be used, as appropriate, and details will be described in the SAP.

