2.1. Multiplicity Adjustment

For primary and key secondary efficacy objectives, the details of type I error control strategy are illustrated in [Figure GPHL.2.1](#). Both efficacy estimand and treatment regimen estimand will be used to assess these objectives. As they are intended for different purposes, no multiplicity adjustments will be made for conducting separate analyses relative to the efficacy and treatment regimen estimands. In addition, no multiplicity adjustments will be made for evaluating other secondary and exploratory objectives, or for safety assessments.

Abbreviations: FG = fasting glucose; H = hypothesis; HbA1c = hemoglobin A1c; HDL-C = high-density lipoprotein cholesterol; Non-HDL-C = non high-density lipoprotein cholesterol; p = pooled dose; SBP = systolic blood pressure; WC = waist circumference; WL = weight loss.

Figure GPHL.2.1. Type 1 error control strategy for primary and key secondary efficacy endpoints.

3. Analysis Sets

For purposes of analysis, the following populations are defined:

Table GPHL.3.1. Description of Analysis Datasets

Population	Description
Entered	All participants who sign informed consent
Randomized	All participants who are randomly assigned a study drug.
Modified Intent-to-Treat (mITT)	All randomly assigned participants who are exposed to at least 1 dose of study drug. Participants will be included in the treatment group to which they were randomized.
Efficacy Analysis Set (EAS)	For glycemic control related endpoints: Data obtained during treatment period from mITT, excluding data after initiation of rescue antihyperglycemic medication or premature discontinuation of study drug (last dose date + 7 days). For other endpoints: Data obtained during treatment period from mITT, excluding data after premature discontinuation of study drug (last dose date + 7 days).
Full Analysis Set (FAS)	Data obtained during treatment period from mITT, regardless of adherence to study drug or initiation of rescue antihyperglycemic medication.
Safety Analysis Set (SS)	Data obtained during the treatment period plus safety follow-up period from mITT, regardless of adherence to study drug or initiation of rescue antihyperglycemic medication.

Unless otherwise specified, for analyses guided by the treatment regimen estimand, the FAS will be used; for analyses guided by the efficacy estimand, the EAS will be used; for safety analysis, the SS will be used.

4. Statistical Analyses

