4.4.2.1. Additional Secondary Efficacy Analyses

Table GPHL.4.3. Secondary Measures (Not Controlled for Type 1 Error)

Objective	Relative to the efficacy measure:	Analysis conducted in a manner similar to:	Additional Information
compare tirzepatide 10 mg and/or 15 mg QW with placebo at 72 weeks:	Mean change in body weight (kg) from randomization	MMRM model in Section 4.3.2.2	LSM estimates through 72 weeks will be plotted by study treatment.
	Mean change in BMI (kg/m ²) from randomization	MMRM model in Section 4.3.2.2	Baseline BMI (kg/m ²) will be used as a covariate. LSM estimates through 72 weeks will be plotted by study treatment.

Objective	Relative to the efficacy measure:	Analysis conducted in a manner similar to:	Additional Information
	Mean change in 7-point SMBG from randomization	MMRM model in Section 4.3.2.2	Baseline SMBG value will be used as a covariate and baseline HbA1c group ($\leq 8.5\%$, $> 8.5\%$) will be used as a fixed effect. In addition to the analyses on each of the 7-points, similar analyses will be done for the 2-hour morning, midday, and evening meal excursions, the mean of all meals 2-hour excursion, the mean of all 7-point measurements, the mean of all pre-meal measurements, and the mean of all 2-hour postprandial measurements.
	Mean change in fasting insulin from randomization	MMRM model in Section 4.3.2.2	Baseline fasting insulin will be used as a covariate. Estimated means through 72 weeks will be plotted by study treatment. Log transformation will be adopted for fasting insulin.
	Mean change in IWQOL-Lite-CT Physical Function composite (PF) score from randomization	ANCOVA model	Terms of treatment, stratification factors, and baseline IWQOL-Lite CT PF score will be used as a covariate. Missing data will be imputed using LOCF method.
	Mean change in SF-36v2 acute form physical functioning domain (PF) score from randomization	ANCOVA model	Same as above but using baseline SF-36 v2 acute PF score as a covariate.
	Mean change in EQ-5D-5L utility score and VAS score from randomization	ANCOVA model	Same as above but using baseline EQ-5D-5L utility score and VAS score as a covariate, respectively.
compare tirzepatide QW (all doses combined) with placebo at 72 weeks	Mean change in DBP (mmHg)	MMRM model in Section 4.3.2.2	All tirzepatide doses will be pooled together. LSM estimates through 72 weeks will be plotted by study treatment.

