4.6. Safety Analyses

Unless specified otherwise, safety assessments will be based on the SS (Table GPHL.3.1). All events that occur between the first dose date of study drug and the end date of study participation will be included, regardless of the adherence to study drug.

The statistical assessment of homogeneity of the distribution of categorical safety responses between tirzepatide doses and placebo will be conducted using Fisher's exact test, unless specified otherwise.

For selected continuous safety parameters, the mean change from baseline versus placebo will be assessed via a MMRM using REML. Data from scheduled visits will be utilized for this analysis. Unless specified otherwise, the model will include country/pooled country, sex, type of AHM used at randomization, treatment group, visit and treatment-by-visit interaction as fixed effects, and baseline value of the safety parameter as a covariate. To model the covariance structure within participants, the unstructured covariance matrix will be used. If this model fails to converge, the covariance structures specified in Section 4.3.2.2 will be tested in order until convergence is met. If the data does not warrant the MMRM model, then ANCOVA model will be conducted.

For selected safety parameters, time-to-first-event analysis via the Cox-proportional hazards model may be conducted. Participants without the event will be censored at the end of study participation. For participants experiencing the event, the “time-to-first-event” will be the time (in weeks) from first dose to first occurrence of the event.

Where necessary, the rate of events will be analyzed using a generalized linear mixed-effects model assuming the number of events follow a negative binomial distribution and with treatment as a fixed effect. The logarithm of days during the active treatment period will be adjusted as an offset to account for possible unequal treatment duration of follow-up among participants.

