4.6.5.11. Renal Safety

Laboratory measures related to renal safety will be analyzed as specified for laboratory measurements in Section 4.6.3.6.

Two shift tables examining changes in renal function from baseline to postbaseline will be created. A min-to-min shift table of eGFR estimated by the Chronic Kidney Disease Epidemiology Collaboration (CKD-EPI) equation with units mL/min/1.73 m², using categories (<30, ≥30 to <45, ≥45 to <60, ≥60 to <90, and ≥90 mL/min/1.73m²). A max-to-max shift table of urine albumin-to-creatinine ratio (UACR), using the categories UACR <30 mg/g, 30 mg/g ≤ UACR ≤300 mg/g, UACR >300 mg/g (respectively, these represent normal, microalbuminuria, and macroalbuminuria).

Mixed model repeated measure analyses for eGFR and UACR will be provided. Log transformation will be performed for UACR.

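### Read literally, the pancreatic-enzyme MMRM in SAP 4.6.5.1.1 fixes the log-baseline slope at 1 and leaves out the stratification factors, which can cost some precision

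*SAP*

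**What the plan says.** SAP 4.6.5.1.1 (Pancreatic Enzyme) fits each enzyme by an MMRM "with a log transformed (postbaseline measure/baseline measure) response variable and treatment, nominal visit, treatment-by-nominal visit interaction as fixed effects". It names no baseline covariate and none of the randomisation strata.

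SAP 4.6 (Safety Analyses) gives a default MMRM for continuous safety parameters. Its fixed effects start with country/pooled country, sex and type of AHM used at randomization, and continue with "treatment group, visit and treatment-by-visit interaction as fixed effects, and baseline value of the safety parameter as a covariate". The default gives way where a section specifies something different.

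Protocol 9.4.1 describes the general MMRM as having treatment, visit and their interaction, together with "stratification factors and baseline measurement as a covariate".

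The other laboratory MMRMs list no terms of their own, so the SAP 4.6 default governs them. SAP 4.6.3.6 says only that MMRM or ANCOVA "will be used for the analysis during the treatment period for the continuous measurements for selected lab tests". SAP 4.6.5.11 says: "Mixed model repeated measure analyses for eGFR and UACR will be provided. Log transformation will be performed for UACR".

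On error control, SAP 2.1 states that "no multiplicity adjustments will be made for evaluating other secondary and exploratory objectives, or for safety assessments".

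**The concern.** A log ratio is the log follow-up value minus the log baseline value. A model for it that contains no baseline term therefore assumes that each unit of log baseline carries over in full to follow-up. When the true slope is below 1, as regression to the mean usually makes it, that assumption leaves avoidable noise in the treatment comparison. Leaving out the randomisation factors can add a little more.

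The enzyme section is the only safety MMRM in the SAP that lists its own terms. It gives no reason for a shorter list than the default. The log scale is not a reason, because the log UACR model keeps the default. Two programmers could fit different models from this text.

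The stake is the width of the intervals for the between-arm enzyme differences. No primary or key secondary conclusion depends on it.

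**Working it through.** The SAP states no power, SE or sample size for the enzyme model, so there is no planned figure to reproduce.

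**Inputs.** From the documents: the model terms above and 300 participants per arm, or 900 × 0.75 = 675 in total after the assumed 25% dropout (SAP 5). Assumed, because the documents are silent: rho, the log-scale correlation of baseline with follow-up; k, the follow-up SD divided by the baseline SD; R², the share of residual variance explained by the strata; and the number of countries.

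**Step 1, fixed slope.** Let X be log baseline (SD 1) and Y log follow-up (SD k). The response is Y − X. Variance per participant:
- as written: 1 + k² − 2·rho·k
- with log baseline fitted at that visit: k²(1 − rho²)
- difference: (1 − rho·k)², which is never negative and is zero when the true slope rho·k equals 1.

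The SE ratio is the square root of the first divided by the second. For rho 0.7 and k 1: sqrt(0.60/0.51) = 1.085.

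| rho | k 0.8 | k 0.9 | k 1.0 | k 1.1 | k 1.2 |
|---|---|---|---|---|---|
| 0.5 | 1.323 | 1.224 | 1.155 | 1.106 | 1.072 |
| 0.6 | 1.288 | 1.187 | 1.118 | 1.072 | 1.042 |
| 0.7 | 1.262 | 1.154 | 1.085 | 1.042 | 1.017 |
| 0.8 | 1.250 | 1.126 | 1.054 | 1.016 | 1.002 |
| 0.9 | 1.282 | 1.111 | 1.026 | 1.000 | 1.012 |

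With equal SDs (k = 1) the SE as written is 15%, 12%, 8%, 5% and 3% larger at rho 0.5, 0.6, 0.7, 0.8 and 0.9. In sample-size terms at rho 0.7, the adjusted model with 225 × 0.85 = 191 per arm matches the written model with 225.

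A simulation agreed (three post-baseline visits, unstructured covariance, one common slope, 225 per arm, k = 1, complete data, 20,000 runs). The SE ratios were 1.156, 1.085 and 1.024 at rho 0.5, 0.7 and 0.9. Both models were unbiased.

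**Step 2, one slope for all visits.** The SAP 4.6 default has a single baseline slope. If k rises over visits, that pooled slope g is too low for the last visit, where the variance becomes k²(1 − rho²) + (rho·k − g)². With between-visit correlation set equal to rho:
- rho 0.8, k 1.0, 1.1, 1.2: g = 0.859. Last visit 0.5184 + (0.96 − 0.859)² = 0.529, against 0.520 as written. SE ratio sqrt(0.520/0.529) = 0.99.
- rho 0.9, k 0.9, 1.0, 1.1: g = 0.872. Last visit 0.2299 + (0.99 − 0.872)² = 0.244, against 0.230 as written. SE ratio sqrt(0.230/0.244) = 0.97.

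In these cases the common-slope model is 1% to 3% worse than the model as written. A slope for each visit removes this and restores the Step 1 result.

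**Step 3, strata.** If the strata explain R² of 0.02, 0.05 or 0.10, omitting them multiplies the SE by 1/sqrt(1 − R²) = 1.010, 1.026 or 1.054. Including them uses 1 (sex) + 2 (AHM type) + (countries − 1) degrees of freedom. With 15 countries that is 17. If the strata explain nothing, the SE rises by sqrt(672/655) = 1.013 with 675 participants, or sqrt(897/880) = 1.010 with 900. With 5 countries (7 degrees of freedom) the figures are 1.005 and 1.004.

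**The case against.** **Inheritance.** SAP 4.6.5.1.1 lists fixed effects only, and SAP 4.6 names baseline separately, as a covariate. The enzyme section is also silent on REML and the covariance structure, so part of SAP 4.6 must carry over, and the baseline covariate could carry over with it. This stands as a possible reading, and the point is therefore about the text as written. It does not reach the strata, which SAP 4.6 places among the fixed effects, the category that the enzyme section does list. Nor would it settle whether the inherited baseline is on the raw or the log scale.

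**Permitted choice.** SAP 4.6 allows departures, and a fold-change analysis is legitimate. Both are true. No reason for the shorter model is given, however, and the log-ratio response can be kept while the terms are added.

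**The gain is not free or certain.** This stands. Strata use degrees of freedom, and a common baseline slope can be slightly worse at the last visit (Steps 2 and 3).

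**Stronger readings.** A reader might infer that the enzyme comparison is biased. With complete data, randomisation keeps both models unbiased; behaviour under missing data was not examined. A reader might also take the top of the grid, 32%, as the expected loss. Every value above 15% in the equal-SD column's neighbours needs k below 1, that is, follow-up less variable than baseline, and nothing in the documents supports assuming that.

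**Conclusion.** The point holds as a minor one. Taken literally, the enzyme model fixes the log-baseline slope at 1 and drops country/pooled country, sex and AHM type, against both SAP 4.6 and protocol 9.4.1. Whether the baseline covariate was meant to be inherited is unclear; the missing strata are the plainer departure, while the baseline term carries most of the likely gain.

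The effect is on precision only. Under assumed equal SDs, the SE is about 3% larger at rho 0.9 and 15% larger at rho 0.5. It is close to zero where rho·k is near 1. The strata might add 1% to 5% if they explain 2% to 10% of residual variance. None of rho, k, R² or the number of countries is in the documents.

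The analysis lies outside type 1 error control. SAP 4.6.5.1.1 also tabulates enzyme threshold categories, and SAP 4.6.5.1.2 makes adjudication-confirmed pancreatitis the event of special interest. No identified safety conclusion would change.

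**What to change.** In SAP 4.6.5.1.1, before database lock:
- keep the log-ratio response;
- add log baseline enzyme as a covariate, with a log-baseline-by-visit interaction;
- add country/pooled country, sex and type of AHM used at randomization as fixed effects, as in SAP 4.6.

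This takes one sentence and no new data: baseline is already needed to form the ratio, and the strata are recorded at randomisation. The downside is a few degrees of freedom, which could add up to about 1% to the SE if the strata explain almost nothing and there are many countries. If the sponsor prefers the shorter model, the section should say that it replaces the SAP 4.6 terms and why.
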